7.1 Demographics

The demographics will be summarized by treatment group in the ITT Set, Safety Set and **CCI** [REDACTED]. The following variables will be included:

- Age (Years)
- Age group (18 to 45; >45 to 65; >65 to 80; >80)
- Sex (Male, Female)
- Ethnicity (Hispanic or Latino, Not Hispanic or Latino, Unknown or Not reported)
- Race (American Indian or Alaska Native, Asian, Black or African American, Native Hawaiian or Other Pacific Islander, White, Other, Multiple or Not reported)
- Race group (White, Black, Asian, Other)
- Region (US; Excl-US)
- Pre-dialysis weight (kg), Height (cm) at baseline

Status of habitual tobacco use (Never, Former, Current), status of habitual alcohol use (Never, Former, Current), and history of tuberculosis in the past will also be summarized by treatment in the same table as Demographics.

Subject demographics will be presented in a listing.

7.2 Baseline Disease Characteristics

The following baseline disease characteristics will be summarized by treatment group in the ITT Set, Safety Set and **CCI** [REDACTED] :

- Duration of end-stage kidney disease (ESKD) (months)
- Duration of hemodialysis (months)
- Duration of hemodialysis (\leq 1 year; >1 year to 3 years; >3 years)
- Hemodialysis access location (AVF/AVG/Catheter)
- Kt/V result
- Duration of pruritus (months)
- Duration of pruritus (\leq 3 months; >3 to 12 months; >12 months)
- With or without prior or concomitant systemic anti-pruritus treatment

- Cause of chronic kidney disease (CKD) (Hypertension, Diabetes, Glomerulonephritis, Cystic disease, Urologic, Congenital/hereditary, Other)
- Investigator's global assessment (IGA) of CKD-aP skin status
- Weekly Average of WI NRS score
- Severity of pruritus/WI NRS group (5 to 7; >7 to 10)
- Weekly Average of SD NRS score
- CCI [REDACTED]
- [REDACTED]
- [REDACTED]
- [REDACTED]

Baseline disease characteristics will be also presented in a listing.

7.3 Alcohol and Tobacco Usage

Smoking status and alcohol consumption status will be summarized together with demographics characteristics (see section [7.1](#)).

7.4 Childbearing Potential Status, Methods of Contraception and Reproductive Status

Childbearing Potential Status, Methods of Contraception and Reproductive Status will be listed and summarized.

7.5 Medical History

The number and percentage of subjects with any medical history will be summarized by treatment and for each body system by system organ class (SOC) and preferred term (PT). SOC will be sorted in decreasing order of frequency based on the total number of subjects of all treatment groups and within each SOC, PT will be presented in decreasing order of frequency. Percentages will be calculated based on number of subjects in the ITT Set.

Subject medical history data including specific details will be presented in a listing. Body systems will be included as recorded on the CRF.

Medical Dictionary for Regulatory Authorities (MedDRA) dictionary Version 24.1 or higher will be used for reporting and will be described in the relevant table and listing footnotes.

8 Treatments and Medications

8.1 Prior and Concomitant Medications

All medications used within 3 months prior to the date of screening through to the end of study will be collected on the CRF. All medications will be coded according to the World Health Organization drug dictionary Global B3 September 2021 or higher. The medication names will be coded according to the Anatomical Therapeutic Chemical (ATC) class level 4, and preferred terms provided in the dictionary.

A prior medication is defined as any medication that is taken within 3 months prior to the date of the first treatment injection, that is stopped prior to the date of the first treatment injection. A concomitant medication is defined as any existing therapy ongoing at the time of the first treatment injection, or any changes to existing therapies during the course of the study, or any new therapies the subject received since the date of the first treatment injection.

For missing start or end dates, the rules stated in section 4.1 will be followed. Though note that, for treated subjects, if the start date is completely missing and end date is not prior to the first treatment injection, then the medication will be classified as concomitant. If the end date is missing, then the medication will be classified as ongoing. Medications for which the start and end dates are missing will be classified as concomitant. All medications of not treated subjects will be classified as prior.

Prior medications will be summarized by providing the number and percentage of subjects by ATC class level 2, ATC class level 4 and preferred term overall and for each treatment. ATC class level 2 and ATC class level 4 will be sorted in decreasing order of frequency based on the total number of subjects who take each medication in the total column. In the same way, preferred terms within each drug class will be presented in decreasing order of frequency based on the total of all treatment groups. In addition, the total number of prior medications and the number and percentage of subjects receiving at least one prior medication will also be presented in this table. If a subject has multiple medications for a given preferred term the subject will only be counted once. A similar table will be presented for concomitant medications.

All summaries will be performed using the ITT Set. Prior and concomitant medications will be presented in a listing for the ITT Set.

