12.5 Prior and Concomitant Therapy

Prior therapies are defined as therapies that have been stopped within the three months before the screening visit, unless relevant to the inclusion/exclusion criteria. Whenever possible, all prior therapies for CKD-aP should be documented.

Concomitant therapies/medications are defined as follows:

- Any existing therapies ongoing at the time of the screening visit,
- Any changes to existing therapies (such as changes in dose, formulation or application frequency) during the course of the study, or
- Any new therapies received by the subject since the screening visit.

The following two categories are to be considered for prior and concomitant therapies:

- Drugs/Therapies include but are not limited to prescription, over-the-counter, birth control pills/patches/hormonal devices, vitamins, moisturizers, sunscreens, herbal medicines/supplements, vaccines (emergency or seasonal), and homeopathic preparations.
- Medical and surgical procedures (e.g., phototherapy, exodontia). Procedures whose sole purpose is diagnosis (non-therapeutic) are not included.

Prior and concomitant therapies for drugs/therapies or for medical/surgical procedures are to be recorded in the appropriate eCRF.

Concomitant therapies are to be recorded, reviewed, and updated at each visit.

At each visit, investigators should also confirm concomitant therapies for contraception. Contraceptive counseling should occur at screening.

Any new concomitant therapy or modification of an existing therapy may be linked to an AE. In such cases, a corresponding AE form should be completed to account for the new therapy or change in therapy, except in some cases such as dose modification for a chronic condition (see Section 12.3), in which case the medication will be linked to an item in the subject's medical history.

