3.1 Overall Study Design and Plan

This is a randomized, double-blind, placebo-controlled, multicenter, parallel-group study to evaluate the efficacy and safety of nemolizumab in adult subjects with moderate to severe CKD-aP.

Subjects will be randomized in one of the following three arms/groups (two different doses of nemolizumab and a placebo) in a 1:1:1 ratio:

[figure not shown]
- Group 1: 30 mg Nemolizumab Q4W with a 60 mg loading dose at baseline;
- Group 2: 60 mg Nemolizumab Q4W without loading dose at baseline;
- Group 3: Placebo Q4W.

Approximately 84 subjects will be randomized in each nemolizumab group and in the placebo group for a total sample size of approximately 252 subjects.

In order to maintain the blind, all subjects will receive 2 injections at each administration (30 mg + 30 mg or 30 mg + placebo or placebo + placebo).

The study consists of a screening period (up to 4 weeks), a 12-week treatment period, and an 8-week follow up period (12 weeks after the last study drug injection). The screening period will evaluate subject eligibility. At the baseline visit, subjects will receive an initial dose of nemolizumab 60 mg or placebo by two subcutaneous (SC) injections (30 mg + 30 mg, or placebo + placebo). Study drug treatment with either nemolizumab or placebo should start after completion of the hemodialysis treatment (within four hours). Then study drug (i.e., nemolizumab 30 mg, nemolizumab 60 mg or placebo) will be administered via two SC injections (30 mg + placebo, 30 mg + 30 mg, or placebo + placebo) at Week 4 and Week 8 after completion of hemodialysis treatment (within four hours). **CCI** [REDACTED] are to be taken before hemodialysis. [Figure 1](#) below presents the study design:

Figure 1

R = Randomization; * = Visits with study drug administration

Note: All subjects in each arm will receive 2 injections at each administration (either 30 mg + 30 mg, or 30 mg + placebo, or placebo + placebo) in order to maintain the blind

The schedule of assessments is summarized in [Appendix A](#).

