8.2 Prior and Concomitant Medical and Surgical Procedures

All relevant medical and surgical procedures done within 3 months prior to the date of screening through to the end of study will be collected on the CRF. Medical and surgical procedures will be coded according to MedDRA version 24.1 or higher.

For analysis purpose, a prior medical or surgical procedure is defined as any medical or surgical procedure that is done within 3 months prior to the date of first treatment

injection. A concomitant medical or surgical procedure is defined as any medical or surgical procedure started or changed since the first treatment injection.

For missing start or end dates, the rules stated in section 4.1 will be followed. Though note that, for treated subjects, if the start date is completely missing and end date is not prior to the first treatment injection, then the medical or surgical procedure will be classified as concomitant. If the end date is missing, then the medical or surgical procedure will be classified as ongoing. Medical or surgical procedures for which the start and end dates are missing will be classified as concomitant. All medical/surgical procedures of not treated subjects will be classified as prior.

Prior medical or surgical procedures will be summarized by providing the number and percentage of subjects by system organ class (SOC) and preferred term (PT) overall and for each treatment group. In addition, the total number of prior medical or surgical procedures and the number and percentage of subjects undergoing at least one prior medical or surgical procedures will also be presented in this table. A similar table will be presented for concomitant medical and surgical procedures.

All summaries will be performed using the ITT Set. Prior and concomitant medical or surgical procedures will be presented in a listing for the ITT Set.

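### SAP 8.1 and 8.2 collect from 3 months before screening but define 'prior' from 3 months before first injection, so some collected items are in neither summary table

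*SAP*

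**What the plan says.** **Collection.** SAP 8.1: "All medications used within 3 months prior to the date of screening through to the end of study will be collected on the CRF". SAP 8.2 uses the same starting point for relevant medical and surgical procedures.

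**Classification.** In SAP 8.1 the definition of a prior medication reads "any medication that is taken within 3 months prior to the date of the first treatment injection, that is stopped prior to the date" (again, first injection). A concomitant medication is "any existing therapy ongoing at the time of the first treatment injection, or any changes to existing therapies during the course of the study", or a therapy new since the first injection. SAP 8.2 defines a prior procedure as "any medical or surgical procedure that is done within 3 months prior to the date" of first injection, and a concomitant one as started or changed since then. In both sections, everything recorded for an untreated subject counts as prior. There is no equivalent rule for treated subjects.

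**Protocol.** Protocol 12.5 anchors on screening: "Prior therapies are defined as therapies that have been stopped within the three months before the screening visit", with an exception for therapies relevant to eligibility. It adds: "Whenever possible, all prior therapies for CKD-aP should be documented". Its concomitant class begins with "Any existing therapies ongoing at the time of the screening visit".

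**Distance between the anchors.** SAP 3.1: "The study consists of a screening period (up to 4 weeks), a 12-week treatment period". Protocol 10.1 allows up to 72 hours' deviation from the screening window in exceptional circumstances.

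**Use of the classes.** Tables 14.1.6.1 and 14.1.7.1 summarise prior medications and prior procedures. SAP 4.9 and 7.2 use prior or concomitant systemic anti-pruritus treatment as a subgroup and as a baseline characteristic. SAP section 16 declares no change to the protocol's intent.

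**The concern.** The collection window opens before the classification window, by about the length of screening. A record whose stop date lies between the two openings is on the CRF and is prior under Protocol 12.5, but SAP 8.1 gives it no class. For treated subjects, the prior-therapy tables then leave out part of what was collected, and how much depends on each subject's screening length.

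Previous treatment helps to describe this population, so the descriptive tables should show it as collected. The subgroup is the second point at stake. SAP 8.1 is the SAP's only definition of a prior medication. If it is applied to the subgroup, a subject whose only systemic anti-pruritus treatment ended in the gap is classed as without such treatment.

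**Working it through.** The plan states no figure on this point, so there is nothing to reproduce. The check classifies each possible stop date of a treated subject with complete dates.

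**Inputs**
- Collection opens at screening minus 3 months (SAP 8.1, 8.2).
- The SAP prior window opens at first injection minus 3 months (SAP 8.1, 8.2).
- Time from screening to injection is up to 28 days (SAP 3.1), or 31 days with the 72-hour deviation (Protocol 10.1). Shorter intervals of 7, 14 and 21 days are assumed to show the range.

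**Worked case.** Screening is on 18 August 2023 and first injection on 15 September 2023, 28 days later. Collection opens on 18 May and the SAP prior window on 15 June. A drug stopped on 1 June is collected and is prior under Protocol 12.5. It was not taken in the SAP's 3 months, so it is not prior under SAP 8.1. It ended well before screening, so it is not ongoing, changed or new, and therefore not concomitant. The gap runs from 18 May to 14 June, which is 28 days.

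**Gap by screening length.** Four illustrative injection dates were used (the 15th of March, June, September and December 2023). The spread comes from unequal month lengths.

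| Screening (days) | Unclassified stop dates (days) | Share of the 3 months before screening |
|---|---|---|
| 7 | 7 | about 8% |
| 14 | 14 | 15–16% |
| 21 | 18–23 | 20–25% |
| 28 | 25–30 | 28–33% |
| 31 | 28–33 | 32–36% |

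**Share of items.** This assumes stop dates spread evenly and 3 months taken as 91 days.
- Denominator: items stopped in the 3 months before screening. 28/91 = 30.8% for a 28-day screening; 14/91 = 15.4% for 14 days.
- Denominator: all items stopped before injection, including those stopped during screening, which SAP 8.1 does class as prior. 28/(91 + 28) = 28/119 = 23.5%; 14/(91 + 14) = 14/105 = 13.3%.

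**After the fix.** With the window opening at screening minus 3 months and closing at first injection, no stop date in the collection window is unclassified at any screening length tested.

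**A related difference.** A drug stopped during screening is concomitant under Protocol 12.5 and prior under SAP 8.1. Nothing is lost, but the two documents sort it differently.

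**The case against.** The strongest defence is that the SAP's rule is a deliberate analysis choice. It gives every treated subject the same 3-month look-back from first dose, the collected data fully cover that look-back, and collecting more than is tabulated is not an error. Protocol section 19 also lets the SAP prevail where the two documents differ.

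Part of this stands. The constant look-back is a real property, and the fix gives it up. Precedence also settles the difference from Protocol 12.5. It does not settle the mismatch inside SAP 8.1, where the collection and classification windows disagree and the SAP does not say that the records in between are left out on purpose. Section 16 also says nothing about moving the anchor.

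Several limits also stand. Untreated subjects are unaffected. A missing end date makes the drug ongoing, and SAP 4.1 generally imputes partial stop dates to the end of the month or year, which can move records out of the gap. Most washouts for anti-itch treatments in Protocol Table 1 are 1, 2 or 4 weeks, so many stop dates may fall close to screening, inside the SAP window.

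A reader might go further in four ways that the documents do not support:
- **The records vanish from the report.** SAP section 4 has all collected data listed, and Listings 16.2.4.5 and 16.2.4.6 cover medications and procedures.
- **Washed-out therapies are hit much harder.** For a 4-week washout, even spread over the remaining 91 − 28 = 63 days would give 28/63 = 44%. The documents give no distribution of stop dates, and stopping just in time for the washout would lower that share.
- **All older CKD-aP therapies are lost because of the anchor.** Those that ended more than 3 months before screening are generally outside Protocol 12.5's own window too, and SAP 8.1 does not describe collecting them.
- **The subgroup is misclassified.** SAP 4.9 refers to a list from medical experts and does not cite 8.1. Membership is prior or concomitant, so users of permitted stable background drugs that are on the list count anyway.

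**Conclusion.** The point holds as a small defect of specification. For treated subjects with a known stop date, SAP 8.1 and 8.2 leave unclassified a span of collected history about as long as screening, up to about 4 weeks. The certain effect is on two descriptive tables.

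The shares of about 31% and 24% assume a full 28-day screening and evenly spread stop dates. Shorter screening gives less, and stopping close to screening gives less again. The documents support neither assumption, so the figures show scale and are not estimates.

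The effect on the anti-pruritus subgroup is conditional on the 8.1 definition being used there. It would then reach only a subject with no other qualifying treatment, prior or concomitant. No primary or key secondary test is affected, and with randomised arms there is no reason to expect the gap to differ systematically between groups.

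**What to change.** - **SAP 8.1:** define a prior medication as one taken at any time from 3 months before screening and stopped before the first treatment injection.
- **SAP 8.2:** make the same change of anchor, so that a prior procedure is one done from 3 months before screening and before the first treatment injection.
- **SAP 4.9 and 7.2:** state that the prior part of the systemic anti-pruritus grouping uses this definition. The experts' list then decides which drugs count, and 8.1 decides when.
- **SAP section 16:** record the change, and note that drugs stopped during screening are classed as prior in the SAP but as concomitant in Protocol 12.5.
- **Older CKD-aP therapies:** summarise those that ended before the collection window separately, or only list them. The protocol asks for them where possible, so their collection is not systematic. Counting every CRF record as prior would mix them with a complete 3-month history and make subgroup membership depend partly on how thoroughly sites took histories.

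The cost is a few sentences before unblinding and no new data. The downside is small: the look-back from first injection becomes 3 months plus the subject's screening length, so it varies between subjects by up to about 4 weeks.

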8.2 Prior and Concomitant Medical and Surgical Procedures

All relevant medical and surgical procedures done within 3 months prior to the date of screening through to the end of study will be collected on the CRF. Medical and surgical procedures will be coded according to MedDRA version 24.1 or higher.

For analysis purpose, a prior medical or surgical procedure is defined as any medical or surgical procedure that is done within 3 months prior to the date of first treatment

injection. A concomitant medical or surgical procedure is defined as any medical or surgical procedure started or changed since the first treatment injection.

For missing start or end dates, the rules stated in section 4.1 will be followed. Though note that, for treated subjects, if the start date is completely missing and end date is not prior to the first treatment injection, then the medical or surgical procedure will be classified as concomitant. If the end date is missing, then the medical or surgical procedure will be classified as ongoing. Medical or surgical procedures for which the start and end dates are missing will be classified as concomitant. All medical/surgical procedures of not treated subjects will be classified as prior.

Prior medical or surgical procedures will be summarized by providing the number and percentage of subjects by system organ class (SOC) and preferred term (PT) overall and for each treatment group. In addition, the total number of prior medical or surgical procedures and the number and percentage of subjects undergoing at least one prior medical or surgical procedures will also be presented in this table. A similar table will be presented for concomitant medical and surgical procedures.

All summaries will be performed using the ITT Set. Prior and concomitant medical or surgical procedures will be presented in a listing for the ITT Set.

8.3 Rescue Therapies

Rescue therapies are defined as below and include the following treatments:

- Antihistamines (new or increased dose): For those given as needed (“PRN”), at baseline, rescue of antihistamine is defined as that with an increase by $\geq 75\%$ in the total weekly dose relative to the dose during the last week of screening administered for ≥ 1 week.
- Gabapentin (new or increased dose) administered for ≥ 1 week.
- Selected Opioids: Nalbuphine or kappa opioid agonists (e.g., difelikefalin, nalfurafine), one or more doses.
- Ultraviolet radiation therapy: one or more treatments.

For the purpose of efficacy analyses (including sensitivity and supplementary analyses), that are not based on Observed Case (OC), subjects receiving any rescue therapies will be considered as treatment failures. Efficacy data collected after the use of rescue therapies will be set to the worst possible value for continuous variables and subject’s binary response will be imputed as “Non-responder” prior to conducting the MI and Tipping Point analysis.

Investigator assessments of efficacy should be performed before initiating rescue therapy. Subjects requiring rescue therapy between scheduled visits should return to the clinic (unscheduled visit) for investigator assessment of efficacy before starting rescue therapy.

Rescue medications will be summarized for the ITT Set, by rescue therapy type (topical, systemic) and, within each rescue type, by ATC class level 2, ATC class level 4 and preferred term overall and for each therapy. ATC class level 2 and ATC class level 4 will be sorted in decreasing order of frequency based on the total number of subjects of all treatment groups and within each drug class, preferred terms will be presented in decreasing order of frequency.

Rescue procedures will be summarized for the ITT Set, by rescue therapy type (phototherapy) and by SOC and PT overall and for each therapy. SOC will be sorted in decreasing order of frequency based on the total number of subjects of all treatment groups and within each SOC, PT will be presented in decreasing order of frequency.

Rescue therapies data including specific details will be presented in a listing.

The time to first rescue therapy will be analyzed using Kaplan-Meier survival functions that will be compared between treatment groups by using the log-rank test. The number and proportion of events and censoring, point estimates of the median, Q1 and Q3 with the corresponding 97.5% CI will be presented and Kaplan-Meier curves will also be provided. Subjects who do not use any rescue therapy during the study will be censored and date of end of participation will be used as censoring date.

